#### **7.5.3 Serious adverse events**

A **summary of all SAEs** will be provided by pharmacovigilance.

## **7.6 Quality of life assessment**

Quality of life is assessed using the EORTC QLQ-C30 and HCC18 questionnaires.

The scores of these questionnaires at inclusion will be described using standard statistics.

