Statistical methods	
The assumptions are:
 
 • H0: a proportion of patients with an objective response at 6 months of 25% or less is not acceptable • H1: A proportion of patients with an objective response at 6 months of more than 25% would show the effectiveness of the treatment. A rate of 40% is hoped for. 
Using a 2-stage Fleming design (Fleming, 1982) with a one-sided alpha risk of 5% and power of 90%, it is necessary to include 86 treated and evaluable patients.
 
At the 1^{ère} stage: 43 patients will be included
 
 - If 10 or fewer patients have an objective response, the trial will be stopped for futility (H1 rejection) - If 18 or more patients have an objective response, the trial will be stopped for efficacy (rejection of H0) 
If not, we will go to 2^{ème} step and include 43 additional patients.
 
If 29 or more patients have an objective response, the treatment will be declared effective (rejection of H0)
 
Taking into account a rate of 5% of lost to follow-up or not assessable, 91 patients will be included. The decision rules will be adapted based on the number of evaluable patients actually included.

Biological studies	Analysis of VEGF level by ELISA technique and progastrin level then correlation with tumor and non-tumor liver volumes.
Number of subjects needed	91
Planned study period	
Rate of 10 patients per month (1 patient per month per center - 10 centers)
 
Expected start date of inclusions: September 2014.
 
Expected completion date of inclusions (stage 2): July 2016
 
Expected completion of study: January 2020

EXAMINATION AND FOLLOW-UP SCHEDULE

	BEFORE TREATMENT	DURING TREATMENT with CHE			AFTER 6 MONTHS (patient follow-up)	
	Within 28 days before 1 ^{ière} HEC and before inclusion	Before each HEC	After each HEC	At 6 months after inclusion	1 ^{ière} year every 3 months	2 ^{ième} year every 6 months
Clinical and biological informed consent	X					
CLINICAL EXAMINATION						
Weight, height, pain assessment (VAS)	X	X			X	
General status WHO	X	X			X	
Child-Pugh if associated cirrhosis and BCLC score	X					
Quality of life (QLQ-C30 and HCC-18)	X	X				
Description of the disease and medical history	X	X				
Toxicity assessment (NCI-CTC v4.0)			X	X		
MORPHOLOGICAL EXAMINATIONS*** (IN FRENCH ONLY)						
Hepatic MRI	X		X	X	X****	X****
Ultrasound of the liver					X****	X****

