- Digestive disorders: nausea, vomiting, diarrhea
- Stomatitis, esophagitis
- Elevated liver enzymes and bilirubin in 20-30% of cases
- Skin rash
- Acute heart rhythm disturbances, acute or late heart failure (rare before a cumulative dose of 93 mg/m²)
- Red coloration of the urine 24 to 48 hours after treatment.

As with other DNA altering anticancer agents, myelodysplastic syndromes and acute myeloid leukemias have been observed after combination therapy with anthracycline.

In case of idarubicin-related effects, no dose adjustment of idarubicin for loading the microbeads is planned. The chemoembolization session is then postponed or cancelled.

VII. MONITORING DURING AND AFTER TREATMENT

VII.1 Before each HEC

- Complete clinical examination: weight, vital signs, WHO general condition (which should be 0 or 1), pain assessment (VAS)
- Biological work-up: CBC/platelets, blood ionogram, creatinine, albumin, transaminases (AST, ALT), alkaline phosphatases (ALP), GGT, total and conjugated bilirubin, PT
- Adverse event evaluations of previous HECs according to NCI CTC version 4.0
- Quality of life questionnaires (QLQ-C30 and its module HCC18)

Prior to the session, the investigator should ensure that the patient has adequate hepatic and hematological function:

- Bilirubin ≤ 1.5 mg/dL, PNN $\geq 1,000/\text{mm}^3$, platelets $\geq 50,000/\text{mm}^3$, creatinine level $\leq 150 \mu\text{mol/L}$
- Hepatopoietic flow, thrombosis is considered significant if it involves at least 3 segments. The procedure is then contraindicated. A Doppler is strongly recommended before the embolization sessions to ensure that the procedure can be performed. It is recommended to evaluate these criteria according to the habits of the center.

For patients participating in the translational study: blood sampling for translational study (see paragraph IX)

VII.2 After each HEC

Hepatic MRI (or CT scan in case of contraindication to MRI) will be performed 4 to 6 weeks after each chemoembolization to assess their effectiveness.

Assessment imaging at 6 months from the date of inclusion MUST be performed regardless of the time of last HEC to assess the primary endpoint of the study.

Target measurements will be done according to mRECIST v1.1 to assess the primary endpoint of the study and according to EASL criteria to assess the secondary endpoint (Appendices 4 and 5).

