If 29 or more patients have an objective response, the treatment is declared effective (rejection of H0)

Taking into account a 5% rate of patients lost to follow-up or not evaluable, **91 patients** will be included. The decision rules will be adapted based on the number of evaluable patients actually included.

XII.4 Statistical analysis plan

A statistical analysis plan will be written prior to freezing the database.

Analysis Populations:

The characteristics of the patients included in the study will be described in strict intention-to-treat (ITT). Efficacy analyses will be performed on a modified intention-to-treat (mITT) basis: all evaluable patients included in the study regardless of eligibility criteria. A patient is considered evaluable if he/she has had at least one chemoembolization and one post-treatment evaluation.

Population evaluable for safety:

The ITT population that received at least one chemoembolization.

Statistical analysis:

The description of the variables will be done using percentages (95% confidence interval) for qualitative variables and using mean (standard deviation) and median (Min-Max) as well as the inter-quartile range (Q1-Q3) for quantitative variables.

The estimation of censored data will be done by the Kaplan Meier (KM) method. Times will be described by medians and rates at different time points with their 95% confidence intervals. The median follow-up time will be calculated using the reverse Kaplan Meir method.

XII.5 Independent Committee

An independent committee composed of 1 clinician / 1 methodologist-statistician / 1 pharmacovigilant expert / 1 radiologist will be set up before the beginning of the trial. It will meet regularly during the course of the study according to the rate of inclusion.

It will have to rule on the declared ADRs. It can also be seized at any time by the Sponsor in case of significant facts on the tolerance (ADRs and AEs) of the treatment.

XIII. JUSTIFICATION OF THE TEST

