##### **3.1.2 Secondary objectives**

The secondary objectives of this study are to evaluate:

- The 6-month objective response rate (mRECIST) assessed by the investigator
- 6-month objective response rate (EASL)
- Time to treatment failure
- The best response according to mRECIST
- Progression-free survival
- Overall survival
- Treatment tolerance
- Quality of life (QLQ-C30 questionnaires and its HCC18 module specific to HCC)

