## 6.5 Baseline definition

Baseline measurements are the last measurements taken at inclusion. In the event of missing data, the last measurement taken before the first treatment is used.

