## 6.6 Statistics

**Quantitative variables** will be described using headcount, median, mean, standard deviation of the mean, minimum, maximum and inter-quartile range (Q1-Q3). Quantitative variables can be categorized using their median or a cut-off known from the medical literature.

**Categorical variables** will be described using percentages, and if necessary their bilateral 95% confidence intervals (calculated using the exact method).

Missing values are not taken into account when calculating frequencies and percentages.

The **confidence intervals** provided will be two-sided 95% confidence intervals, except for the main criterion where a one-sided 95% confidence interval will be given.

**Survival data** will be estimated and plotted using the Kaplan-Meier method (Kaplan and Meier, 1958). This will be described by the median and rates calculated at different times. 95% confidence intervals will be provided. Confidence intervals for rates will be constructed from the Greenwood variance calculated using the log-log transformation.

The median follow-up time is calculated using the reverse Kaplan-Meier method (Shemper, 1996).

The treatment hazard ratio will be estimated using a univariate Cox model (Cox, 1984). The hypothesis of proportionality of rates will be tested using the graphical representation and test based on Schöenfeld residuals (Grambsch, 1994); the linearity of the effect of continuous variables on risk will be assessed using the graphical representation of martingale residuals. Confidence intervals for Cox model coefficient estimates will be calculated using Wald's method.

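### SAP 7.6 specifies a description of quality of life at inclusion only; the forms due before the second, third and fourth chemoembolization have no specified analysis

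*SAP*

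**What the plan says.** SAP 3.1.2 lists among the secondary objectives "Quality of life (QLQ-C30 questionnaires and its HCC18 module specific to HCC"). Protocol I.2 does the same, and Protocol XII.2.2 repeats it as a secondary endpoint without a definition, time point or method.

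Collection is set out in the protocol. Section III asks for both questionnaires in the pre-inclusion work-up. Section VII.1 lists, among the items due before each HEC, "Quality of life questionnaires (QLQ-C30 and its module HCC18"). The row for "Quality of life (QLQ-C30 and HCC-18") in the examination and follow-up schedule agrees: it is marked before treatment and before each HEC, and nowhere else.

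The analysis is left to SAP 7.6. After naming the instruments, it says: "The scores of these questionnaires at inclusion will be described using standard statistics". It names no other visit, no change score and no analysis population.

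**The concern.** Scores taken at inclusion describe patients before they are treated. They are a baseline characteristic and say nothing about quality of life under treatment. Patients are nevertheless asked to complete two questionnaires before each further session, and the SAP gives those forms no use.

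Two things are at stake. First, a stated secondary objective would be reported with no information from after treatment starts. Second, if the later forms are analysed anyway, the visits, summaries and denominators will have been chosen without a plan. SAP 4.6.1 shows that the interim result was already known when the SAP text was written.

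**Working it through.** No figure in the plan needs reproducing. The check sets the collection schedule against the analysis text.

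**1. Which scheduled forms are post-treatment?** SAP 4.2 gives 1 to 4 sessions. For a patient who receives k sessions, a form is due at inclusion and before each of the k sessions. The inclusion form and the form before HEC 1 both precede treatment, so the number of post-treatment forms is k − 1:

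| Sessions received (k) | Post-treatment forms (k − 1) | With an analysis specified in SAP 7.6 |
|---|---|---|
| 1 | 0 | none exist |
| 2 | 1 | 0 |
| 3 | 2 | 0 |
| 4 | 3 | 0 |

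**2. Is the form before HEC 1 also lost?** No. SAP 6.5 takes baseline as the last measurement at inclusion and adds: "In the event of missing data, the last measurement taken before the first treatment is used". The form before HEC 1 can serve as that fallback, so the gap is confined to HEC 2, 3 and 4.

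**3. Are other post-treatment forms scheduled?** The schedule table has no quality-of-life mark after each HEC, at 6 months or in follow-up. The table may have been damaged in text extraction, but Protocol VII.2 (after each HEC, including the 6-month imaging) and VII.3 (beyond 6 months) also list no questionnaire.

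**4. Does general text supply the analysis?** Two places come close. SAP 6.6 says that quantitative variables "will be described using headcount, median, mean, standard deviation of the mean, minimum, maximum and inter-quartile range (Q1-Q3"). Protocol XII.4 says: "The description of the variables will be done using percentages (95% confidence interval) for qualitative variables", and goes on to quantitative summaries. Both say how a variable is summarised once it has been chosen. Neither names a quality-of-life visit or a change from baseline. The specific section, SAP 7.6, names inclusion.

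**5. Is a population implied?** For baseline scores, yes. Protocol XII.4 states: "The characteristics of the patients included in the study will be described in strict intention-to-treat (ITT"), and SAP 7.1 uses ITT throughout. For scores under treatment nothing is stated, whereas SAP 7.5 names the tolerance population (SP) for safety.

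**6. Who would contribute?** Under Protocol V.2.3, two sessions are planned from the start only in bilobar disease; otherwise retreatment follows the MRI findings. Under Protocol VI.1, a further session is not recommended after complete response or after progression of a treated tumor, and is not given after attributable grade 3 or 4 non-hematological toxicity. Patients with a form before HEC 2, 3 or 4 are therefore selected on tumor extent, response and tolerance. SAP 4.6.1 reports 46 patients included. The documents do not say how many reached each session, so no precision can be claimed for the added summaries.

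**The case against.** The best defence is that this is an omission and not an error. The objective names quality of life without defining it as change over time, so a description at inclusion does not contradict its wording. SAP 7.6 does not rule out further summaries, and no decision in the trial rests on these scores. The trial is single-arm and stopped at its first stage, and retreated patients are a selected group. Because no form is due after the last HEC or at the 6-month visit, the deeper limit lies in the collection schedule, which SAP wording cannot repair.

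Most of this stands, and it sets the weight of the point. A reader might infer that the SAP contradicts the protocol or forbids any later quality-of-life analysis; neither document supports that. A reader might also infer that every patient has three unused post-treatment forms. Three is the maximum, and a single-session patient has none. Nor can the unanalysed forms be placed in a fixed span of weeks, because Protocol V.2.3 allows retreatment for recurrence found at later surveillance.

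The defence does not close the gap. Being free to add an analysis later is not the same as specifying one. Selection among retreated patients is a reason to fix denominators and limits in advance, not to leave the forms unmentioned.

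**Conclusion.** The point holds as a gap in SAP 7.6. Of the up to 3 post-treatment forms per patient, none has a specified analysis, so the plan as written reports nothing on quality of life after treatment starts. This rests on reading the schedule table together with Protocol VII.1 to VII.3, which agree, and on treating the general descriptive rules as methods and not as an assignment of visits.

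The weight is modest: a cheap improvement to a secondary objective. The primary endpoint, the stopping decision and the sample size are unaffected. A reader might hope that analysing these forms would show the effect of treatment on quality of life. The design does not support that: there is no control group, and the forms come only from patients who went on to another session.

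**What to change.** Replace the analysis sentence in SAP 7.6 with text along these lines:

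> QLQ-C30 and HCC18 scores at baseline (section 6.5) will be described in the ITT population. In the SP population, scores before HEC 2, 3 and 4 and the within-patient change from baseline (mean with 95% CI, and median) will be described. For each session, the number of patients reaching it and the number of forms completed will be given, with the reasons for not reaching it where these are recorded. These results apply only to patients who went on to a further session, which depends on tumor extent, response and toxicity. No form is scheduled after the last HEC or at 6 months. No treatment effect will be inferred.

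If the restriction to inclusion scores is intended, the SAP should give the reason, and the report should say that quality of life under treatment was not analysed. Either way, date the change and record that it was made after the interim result.

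Cost: a paragraph of SAP text and some additional descriptive output for each questionnaire. The scores need no new collection, because the forms are already scheduled. The same is not shown for the reasons. Protocol VIII lists causes for stopping treatment but not complete response, SAP 7.5.1 covers causes of postponement only, and the case report form is not among the documents; hence the qualifier on recorded reasons. The downside is more output on a selected and possibly small subset. The wording discloses that limit but does not remove it.

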## **8 Quality assurance**

### **8.1 Input**

Data entry and consistency checks will be described in the data management plan.

### **8.2 Base monitoring**

#### **8.2.1 Test analysis**

During the study, one or more test analyses will be carried out. All statistical analyses will be performed on the database extracted at that time. The purpose of these analyses is to :

- anticipate the drafting of statistical analysis programs;
- highlight inconsistencies in patient records not identified by data management rules;
- identify problems not considered when drafting the protocol and statistical analysis plan.

Identified problems requiring modification or clarification of the protocol or analysis plan will be discussed with the coordinator.

#### **8.2.2 Dual programming**

Double programming of the primary and secondary efficacy criteria will be carried out by two different statisticians. Results will be compared, and errors discussed and corrected.
